Regression models will be adjusted by baseline values and stratification factors as covariates, estimates of differences will be generated as marginal effects, derived from bootstrapped mean differences between the groups and the 95% confidence interval. To adjust the analysis for any potential bias that may emerge because participants were recruited to the pilot or efficacy stage of the study, we will employ an individual patient data meta-analysis approach whereby a dichotomous variable indicating pilot or efficacy study is entered into the model as a fixed effect.

Sensitivity analyses will be performed using a pattern mixture approach and multiple imputation to compare the sensitivity of conclusions to varying assumptions about the missing data, particularly whether data is missing at random (MAR) or missing not at random (MNAR) this allows for an assessment of both random and systemic bias.

The usual approach to assessing adherence is to conduct a per protocol analysis, dropping those participants who did not comply with their allocated intervention. However, this approach potentially leads to an underestimate of any true effect. We will conduct a Complier Average Causal Effects (CACE) analysis using an instrumental variable framework. CACE weights the analysis by the ITT treatment effect by the proportion of adherence, this allows the estimation of unbiased treatment effects and maintains the allocation in the analysis.

Secondary outcomes will be analysed in a similar manner, adjusting for baseline values and stratification factors as covariates.

The mechanism of change will be explored using a mediation model approach and incorporating motivation, self-efficacy, and expectancy at 6-months, adjusted for baseline covariates. Allocated group will be included as an interaction term.

Stepwise regression analysis will be performed to model the relationship between pre-randomisation factors and observed outcomes at 6 months, separately for the primary outcome and PDA substance use. Interaction terms with allocation arm will be included in the analysis, and a significance level of 0.1 will be used to determine which factors are to be included in the regression model. Pre-randomisation factors will include gender, age, ethnicity, IMD decile, adverse childhood experiences, anxiety and depression and family cohesion. This analysis will be augmented by an additional analysis including participants in

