factors play in the outcomes observed.” To achieve this, we plan on recording a random sample of interventions, stratified by interventionist and site, and having these independently scored using an established tool for assessing fidelity in behavioural change interventions, the Behavioural Change Counselling Index (Lane, 2002). This instrument provides an overall score and a domain score, for 16 key domains associated with behaviour change, ranging from 1 to 5 where 1 indicates low fidelity and 5 indicates high fidelity. We propose to conduct an analysis to explore the role fidelity, adolescents’ perception of therapeutic alliance and interventionist role legitimacy impact on the outcomes observed. We will employ a stepwise regression model, with the primary outcome as the dependent variable and adjusting for key covariates identified using a variable reduction approach. The results of this analysis will allow a quantification of what fidelity dimensions are most associated with changes in outcomes. This will enable an exploration of whether certain domains are more important than others and should be emphasised in the intervention delivery and, by extension, the training. Allied to this the adolescent perception of therapeutic alliance, assessed using the Therapeutic Alliance Scale for Children (TASC-r) and interventionist perceptions of their confidence and legitimacy in delivering substance use interventions for adolescents, will provide an insight into whether therapist style influences outcomes, and if so what aspects of therapist style are associated with better outcomes.

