The primary analysis will be based on the analysis by treatment allocated (ITT) dataset.

This contains all available data for participants who were randomised, regardless of whether they complied with allocation. This dataset will include participants who were withdrawn/withdrew from the trial post-randomisation. These analyses are a lower bound estimate of treatment effects as they represent the effect of offering an intervention, rather than the effect of receiving the intervention.

The primary outcome is the frequency of offences at 6-months post-randomisation. Prior to analysis we will conduct a series of diagnostic tests and assess the underlying assumptions prior to choosing an appropriate and statistically rigorous regression modelling approach. At this stage we propose an Ordinal Least Squares (OLS) regression approach.

Regression models will be adjusted by the baseline number of offences in the six months prior to randomisation and stratification factors; age group and site, as covariates. The regression model specification is detailed in eq. 1.

Eq. 1

$$OFF6_{i,j} = \alpha + \beta_1(allocation)_{i,j} + \beta_2(OFF0)_{i,j} + \beta_3(age)_{i,j} + \beta_4(site)_j + \beta_4(study)_j \varepsilon_i$$

Where for participant *i* within service *j*; *OFF6* is the number of offences at month-6, *allocation* is the allocated group, *OFF0* is the number of offences in the 6-months prior to baseline score, *age* the age group (10-14 years/ 15-17 years) , *site* the site level dummy variables to adjust for site (Kent/ Cornwall/ Sefton/ Lancashire) fixed effects and *study* the study level (pilot/ efficacy) dummy variable to adjust for study fixed effects and ε_i the individual level error.

Estimates of difference will be generated as a mean difference between the groups and the associated 95% confidence interval.

Secondary outcome analysis

Secondary outcome analysis will be based on the ITT dataset and will be similar to the analysis of the primary outcome. Diagnostic plots for each outcome will be derived and examined to identify the most appropriate regression approach. Where appropriate linear analysis of covariance will be undertaken for continuous normally distributed outcomes, logistic regression with incorporation of covariates for dichotomous variables and fractional covariate regression for proportional outcomes. Covariates will include baseline values for each outcome and stratification factors, site and age group.

Further analyses

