Three exploratory analyses will be undertaken.

The mechanism of change will be explored using a mediation model approach and incorporating motivation (RR), self-efficacy (SCQ-8), and expectancy (SUE) at 6-months, adjusted for baseline covariates. Allocated group will be included as an interaction term.

Stepwise regression analysis will be performed to model the relationship between prerandomisation factors; age, gender, ethnicity, IMD, BFRS, ACEQ, GAD-7, PHQ-9 and observed outcomes at 6 months, separately for the primary outcome and PDA substance use. Interaction terms with allocation arm will be included in the analysis, and a significance level of 0.1 will be used to determine which factors are to be included in the regression model. Prerandomisation factors will include gender, age, ethnicity, IMD decile, adverse childhood experiences, anxiety and depression and family cohesion. This analysis will be augmented by an additional analysis including participants in the intervention arm only using the same prerandomisation factors but also including process measures of adherence, intervention fidelity, therapeutic alliance, interventionist, and interventionist perceptions.

Interim analyses and stopping rules

No interim analyses are planned.

Longitudinal follow-up analyses

Proposed outcomes at each stage of the evaluation

Assessments are conducted at baseline and then at six months post-randomisation, the latter being the primary endpoint. Table 2, indicates outcomes assessed at each end-point.

Outcome	No. of Questions	Baseline	Month 6
Frequency of substance use (Single TLFB item)	1	~	
Time Line Follow-Back 28-day version ¹	0		\checkmark
Wellbeing (WEBWMS)	14	~	~
Quality of Life (EQ5D-5L)	5	\checkmark	\checkmark
Strength & Difficulties (SDQ ²)	25	~	~
Self-report Delinquency (SRDS ^{1,2})		~	\checkmark
Motivation state to change (RR)	1	~	~
Substance Use Expectancy (SUE)	4	~	\checkmark
Self-efficacy (SCQ-8)	8	~	\checkmark
Generalised Anxiety Scale (GAD-7)	7	\checkmark	
Depression - Personal Health Questionnaire (PHQ-A)	8	~	
Adverse Childhood Experiences (ACEQ)	10	\checkmark	
Brief Family Relationships Questionnaire (BFRS)	16	\checkmark	

 1 TLFB28 and SRDS are researcher led questionnaires rather than client self-completed 2 SRDS and SDQ are YEF Core outcomes

Imbalance at baseline

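### The exploratory stepwise models of 6-month offending do not name baseline offences, site or study stage as covariates, so in the intervention-arm model process measures that only track prior offending can be read as active ingredients

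*SAP*

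**What the plan says.** SAP Further analyses gives the candidates for the stepwise models twice. The first list is by instrument: "prerandomisation factors; age, gender, ethnicity, IMD, BFRS, ACEQ, GAD-7, PHQ-9 and observed outcomes at 6 months". The second is in words: "Prerandomisation factors will include gender, age, ethnicity, IMD decile, adverse childhood experiences, anxiety and depression and family cohesion". The Protocol has the same list under Analysis ("Pre-randomisation factors will include gender, age, ethnicity, IMD decile, adverse childhood experiences, anxiety and depression and family cohesion") and again under Exploring Adaptation. Age is the only Eq. 1 covariate that appears. The selection rule is: "a significance level of 0.1 will be used to determine which factors are to be included in the regression model".

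A second model, in the intervention arm only, is built "using the same prerandomisation factors but also including process measures of adherence, intervention fidelity, therapeutic alliance, interventionist, and interventionist perceptions".

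Elsewhere the SAP states its adjustment:

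- Primary outcome analysis: "Regression models will be adjusted by the baseline number of offences in the six months prior to randomisation and stratification factors; age group and site," with a pilot/efficacy dummy added in Eq. 1.
- Secondary outcome analysis: baseline value, site and age group.
- The mediation model, one paragraph before the stepwise models: baseline covariates.

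Two Protocol statements also bear on the point. The Analysis section says that regression models are adjusted for baseline values and stratification factors, and then describes entering the pilot/efficacy indicator. The fidelity section of the process evaluation describes a stepwise model of the primary outcome "adjusting for key covariates identified using a variable reduction approach", without naming the covariates.

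**The concern.** Prior offending is a natural predictor of later offending, and it is available for every participant whose police record is extracted. If it is left out, any factor correlated with it takes on part of its association with the outcome.

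This matters most in the intervention-arm model. Nobody is randomised to attend both sessions, to form a good alliance or to see a particular worker. Young people with more prior offences may attend less or engage less well, and workers may see different mixes of young people. A process measure with no effect of its own could then be selected and read as an active ingredient.

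The results have declared uses. Objective 3 uses the prognostic model to elaborate mechanisms and, where appropriate, revise the logic model. The fidelity section says its results will show whether some domains should be emphasised in delivery and training.

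The point is separate from the choice of stepwise selection: it would remain if every listed factor were simply forced in.

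**Working it through.** **1. The plan's own figure.** The documents give no sample size for the stepwise models. The trial total does reproduce: a standardised difference of 0.3, two-sided alpha 0.05 and 80% power need 175 per arm, 350 in all. Allowing 5% loss, 350 / 0.95 = 368.4, so 369, or 370 with equal arms of 185. The check below therefore uses n = 370 (both arms) and n = 185 (intervention arm).

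**2. Participants with a fidelity score.** Protocol Compliance plans to record 20% of intervention sessions. With two sessions each, 185 × 2 × 0.20 = 74 sessions, so at most about 74 participants have a score.

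**3. Chance that a factor with no effect of its own is retained.** Let rho be the correlation of baseline with 6-month offences, and r that of the factor with baseline offences. Both are assumptions. With baseline offences omitted, the factor's correlation with the outcome is rho × r. By Fisher's z, with m = atanh(rho × r) × √(n − 3), the chance of p < 0.1 (two-sided) is

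1 − Φ(1.645 − m) + Φ(−1.645 − m).

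Example: rho = 0.3, r = 0.2, n = 185. The product is 0.06, m = 0.0601 × √182 = 0.810, and the chance is 0.202 + 0.007 = 0.209.

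| rho | r | n = 370 | n = 185 | n = 74 |
|---|---|---|---|---|
| 0.2 | 0.1 | 0.13 | 0.11 | 0.11 |
| 0.2 | 0.2 | 0.20 | 0.15 | 0.12 |
| 0.3 | 0.2 | 0.31 | 0.21 | 0.14 |
| 0.3 | 0.3 | 0.53 | 0.34 | 0.20 |
| 0.5 | 0.2 | 0.61 | 0.39 | 0.22 |
| 0.5 | 0.3 | 0.89 | 0.65 | 0.36 |

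A simulation with normal variables (4,000 runs per cell) agrees to within about 0.02; its value for the last row at n = 185 is 0.67. A second simulation used overdispersed counts and OLS (1,500 runs per cell). With r = 0.3 and rho of about 0.4 it gave 0.74 at n = 370 and 0.49 at n = 185.

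**4. With baseline offences in the model.** Both simulations return retention to about 0.10 in every scenario (0.09 to 0.11 in the count version).

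**5. Precision.** Take a factor unrelated to baseline offences with 80% power at the 0.1 level. Adjustment divides the noncentrality (1.645 + 0.842 = 2.487) by √(1 − rho²), giving power of 83%, 86% and 89% for rho of 0.3, 0.4 and 0.5. This is a modest gain and not the main argument.

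The check tests one factor at a time and covers only baseline offences. Omission of site and stage was not quantified.

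**The case against.** - **The Protocol may already cover this.** Its adjustment sentence is plural and stands in an undivided Analysis section that also holds the stepwise models. A reader might infer that the plan deliberately leaves baseline offences out; the documents do not support that. Equally, the sentence follows the primary-outcome paragraph, adjustment is restated separately for secondary outcomes, and SAP Further analyses does not repeat it. The exact description is that the Protocol is ambiguous and the SAP silent.
- **A factor that tracks prior offending is not a false predictor.** Adverse experiences or family cohesion may act through prior offending. The marginal correlation is then the same rho × r, but it is a genuine total association, and adjustment would remove it. This stands for the prognostic model, where the choice is between total and conditional association. It does not rescue a reading of process measures as active ingredients, since they arise after randomisation and cannot cause baseline offences.
- **The size is uncertain.** A reader might infer that spurious factors will be reported. The documents give neither correlation, those with four or more previous offences are excluded, which may limit rho, and pilot adherence of 92% leaves little variation in attendance. Retention may be close to nominal.
- **Site may already be represented.** If each worker serves one site (an assumption), the interventionist terms absorb site, and forcing in both creates collinearity. This stands and shapes the fix.
- **The stakes are limited.** The SAP labels these analyses exploratory, and randomisation gives the arm-interaction terms in the both-arm model more protection. Both are true, but the label does not remove the declared uses.

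**Conclusion.** The concern holds as a gap in specification, chiefly for the intervention-arm process model. As the SAP is written, an analyst could follow it exactly and fit that model without baseline offences, site or stage. A process measure that only tracks prior offending could then be retained about 21-67% of the time at n = 185, and about 14-36% for fidelity at n of about 74, against 10% nominal. These ranges rest on assumed correlations (rho 0.3 to 0.5, r 0.2 to 0.3). With rho 0.2 and r 0.1 to 0.2 the chance at n = 185 is only 11-15%.

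For background factors in the both-arm model, the issue is which association is being reported, not that selection is necessarily wrong. The primary and secondary analyses are untouched. The change is worth making because the baseline values are already planned for collection.

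**What to change.** In SAP Further analyses, and in the matching Protocol text (Analysis, the fidelity section and Exploring Adaptation), state that:

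1. Baseline offences, age group and study stage are forced into every stepwise model of the primary outcome before selection. For percent days abstinent, the single baseline frequency item replaces baseline offences.
2. Site is forced in as well, except where interventionists are nested within site. There the interventionist terms (or interventionist within site) carry site, and interventionist effects are not interpreted separately from site.
3. Allocation is also forced into the both-arm prognostic model. Baseline-factor associations are reported with and without baseline offences, labelled conditional and total, so that factors acting through prior offending are not lost.

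The cost is a short paragraph in each document and no new data or change to the 370. The forced terms use about six degrees of freedom (baseline offences 1, age group 1, stage 1, site 3), plus one for allocation in the both-arm model. Some factors may no longer be retained.

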We will assess adherence by recording attendance at each element of the intervention and the control. For those in the intervention group we will assess fidelity by randomly recording 20% of brief intervention sessions stratified by age group, interventionist and site and independently score these using the Behavioural Change Counselling Index (BECCI; (Lane, 2002)). We will ask participants in the intervention arm to complete the short revised therapeutic alliance scale for children after the second intervention session (TASC-r; (Shirk and Saiz, 1992)). There is emerging evidence that the perceptions of interventionists play a key role in the quality of intervention delivered, particularly in terms of their perceived role legitimacy and self-efficacy, both targets of training and ongoing supervision. In order to assess these perceptions, we will ask interventionists to complete the Drug and Drug Using Populations Perceptions Questionnaire (DDPPQ; (Connors et al., 2019)) just prior to training and again 6-months after being trained.

Analysis

In the overall analysis, data from the internal pilot and efficacy study will be combined and analysed blind to group allocation. The efficacy analysis will be conducted and presented in accordance with the CONSORT guidelines. The validity of randomisation will be explored by presenting measures of central tendency and estimates of precision for continuous variables,

and proportions for categorical variables broken down by allocation arm and stratification factors.

The primary outcome is the frequency of non-violent offences at 6-months post-randomisation, and this will be conducted as an analysis by treatment allocated (ITT) and will include all available data maintaining participants as members of their allocated group. Prior to analysis we will conduct a series of diagnostic tests and assess the underlying assumptions prior to choosing an appropriate and statistically rigorous regression model.

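### The exploratory intervention-arm model offers worker identity and a worker-level attitude score to the same stepwise regression, with no provision for participants who share a worker

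*SAP*

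**What the plan says.** The SAP, under Further analyses, describes its exploratory prognostic work as follows: "Stepwise regression analysis will be performed to model the relationship between" pre-randomisation factors and six-month outcomes, separately for the primary outcome and for percent days abstinent (PDA). The selection rule is that "a significance level of 0.1 will be used to determine which factors are to be included in the regression model". It then plans an "additional analysis including participants in the intervention arm only", with the same baseline factors plus "process measures of adherence, intervention fidelity, therapeutic alliance, interventionist, and interventionist perceptions". The Protocol's Analysis section matches this.

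The Protocol's section on exploring fidelity, adherence, differentiation and quality describes the related process model: "We will employ a stepwise regression model, with the primary outcome as the dependent variable and adjusting for key covariates".

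The perception measure is defined in the Protocol under Compliance: "we will ask interventionists to complete the Drug and Drug Using Populations Perceptions Questionnaire" (the DDPPQ), "just prior to training and again 6-months after being trained".

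Neither document names a random effect, a cluster-robust standard error or a worker-level summary for this model. Neither says how many interventionists there are, how interventionist is coded, or which of the two DDPPQ scores is used.

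**The concern.** DDPPQ is a property of the worker, so every young person seen by the same worker carries the same score (or one of two, if both time points are used). The outcome is a property of the young person. However many participants a worker sees, the between-worker information on DDPPQ is limited by the number of workers.

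Offering worker identity and DDPPQ to the same selection procedure creates two difficulties. With worker identity in the model as a set of dummies, a single score per worker adds nothing that the dummies do not already contain. With worker identity out of the model, an ordinary regression counts each participant as independent evidence about DDPPQ.

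At stake is the interventionist-factors part of objective 4, and the Protocol's stated hope of learning whether therapist style influences outcomes. A DDPPQ term that is selected for the wrong reason, or dropped by the software because of aliasing, would answer neither.

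**Working it through.** **Inputs from the documents.** Intervention arm 185 (SAP, Sample size calculations overview). Selection level 0.1 (SAP, Further analyses). Fidelity recorded for 20% of sessions, two sessions per participant (Protocol, Compliance and Intervention). Pilot follow-up for secondary outcomes 88% (SAP, Introduction).

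**Inputs assumed.** Number of workers k = 4, 8, 12 or 20, and worker ICC = 0 to 0.10. The documents give neither.

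**Step 1: the arm size.** Per arm, n = 2(1.960 + 0.842)² / 0.3² = 174.4, so 175 per arm and 350 in total, as stated. Allowing 5% loss, 350 / 0.95 = 368.4, close to the plan's 370 (185 per arm).

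**Step 2: how many participants the model could contain.** 185 is a ceiling.
- PDA at the pilot's follow-up rate: 0.88 × 185 = 163.
- Complete cases on fidelity, if the sample falls on 20% of participants: 0.20 × 185 = 37.
- Complete cases on fidelity, if each of two sessions is sampled independently: (1 − 0.8²) × 185 = 0.36 × 185 = 67.

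**Step 3: both terms in the model.** If worker j has one score s_j, a participant's DDPPQ value is Σ_j s_j × 1(seen by worker j), an exact linear combination of the worker columns. With 8 workers, an intercept plus 7 dummies has rank 8. Adding DDPPQ gives 9 columns, still of rank 8. The same holds for 4, 12, 16 and 20 workers, and for a change score. If the two scores were instead matched to participants by date, the rank would rise to 9 and a within-worker effect could be estimated.

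**Step 4: interventionist not selected.** DDPPQ is tested on 185 − 2 = 183 degrees of freedom, whereas a worker-level test has k − 2. The critical correlation at 0.10 is t / √(df + t²): 0.12 for 185 independent participants, against 0.38 for 20 workers and 0.62 for 8.

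The design effect is 1 + (m − 1) × ICC, with m participants per worker. For 8 workers and ICC 0.05, m = 185 / 8 = 23.1, the design effect is 1 + 22.1 × 0.05 = 2.11, and the effective sample size is 185 / 2.11 = 88.

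**Step 5: false selection at 0.10 when DDPPQ has no effect.** Simulation used a normal outcome of unit variance, near-equal caseloads, one standard normal score per worker and no other candidates, with 10,000 runs per cell. A repeat with 40,000 runs agreed to about one percentage point.

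| Participants | Workers | ICC 0 | ICC 0.01 | ICC 0.05 | ICC 0.10 |
|---|---|---|---|---|---|
| 185 | 4 | 10% | 17% | 37% | 50% |
| 185 | 8 | 10% | 14% | 26% | 36% |
| 185 | 12 | 10% | 13% | 21% | 30% |
| 185 | 20 | 10% | 11% | 17% | 23% |
| 67 | 4 | 10% | 12% | 23% | 31% |
| 67 | 8 | 10% | 12% | 17% | 21% |
| 67 | 20 | 10% | 10% | 12% | 14% |
| 37 | 4 | 10% | 12% | 17% | 23% |
| 37 | 8 | 10% | 11% | 13% | 17% |
| 37 | 20 | 10% | 10% | 10% | 12% |

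Allowing for simulation error, the complete-case range is about 10% to 32%. A regression on worker means held about 10% in every cell.

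**The case against.** **Under-specification.** The plan may be incomplete rather than wrong, because the absence of a worker-level method is inferred from silence. That is fair, but the silence is informative. The SAP names a mixed-effects model where it wants one (Missing data), Eq. 1 carries only an individual-level error, and the one statement on clustering (Levels of confidence and p-values) concerns site and asks for nothing beyond a fixed effect.

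**Not every route fails.** Date-matched DDPPQ scores would be estimable alongside worker dummies, so a reader should not infer that the model must either break down or mislead. But the documents do not say the scores will be matched.

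**Inflation is conditional.** This stands. With no between-worker variation there is none, and at ICC 0.01 it is modest. The 0.1 level is also a rule for entering terms, not a promised error rate. If site is kept in the model and each of four sites has one worker, DDPPQ is aliased with site and the four-worker figures could not arise. Still, the Protocol's own premise (Compliance) is that worker perceptions affect the quality of delivery, so zero between-worker variation would be an odd assumption.

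**Consequences can be overdrawn.** A reader might infer that training content or the logic model would be rewritten on the DDPPQ result. The documents do not support that. The Protocol ties training emphasis to the fidelity domains scored on recorded sessions, and its account of logic-model revision (Exploring Adaptation) does not name DDPPQ. For worker perceptions it promises only insight into therapist style.

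**The analysis is exploratory.** The SAP says so. That limits the weight of the point but does not make the test valid.

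**Conclusion.** The concern holds for this one exploratory model. As written, the DDPPQ effect is not estimable when worker dummies are present with one score per worker, and it is tested at the wrong level when they are absent. The first result is algebraic and needs only that coding. The second needs some variation in outcome between workers.

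Its size cannot be fixed from the documents. It depends on the assumed number of workers and ICC, and on how many participants have complete process data. It ranges from almost no inflation (20 workers, ICC 0.01, 37 to 67 complete cases) to about 50% false selection (4 workers, ICC 0.10, all 185). The simulation isolates the unit-of-analysis problem. It leaves out the other stepwise candidates, baseline offences and site.

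A reader might infer that the trial's treatment effect is compromised. It is not: no between-arm estimate, primary or secondary, depends on this model. The change is worth making before analysis because the result speaks directly to objective 4 and the correction needs no new data.

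**What to change.** In the SAP (Further analyses) and the matching Protocol text:

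- Do not offer interventionist and DDPPQ together as stepwise candidates.
- For offences, keep a random intercept for interventionist in the model throughout, enter DDPPQ as a worker-level covariate, and test it in a linear mixed model with Kenward-Roger or Satterthwaite degrees of freedom.
- For PDA, which is a proportion, use a worker-level summary analysis or another method suited to a proportion that tests DDPPQ at worker level. A regression on worker means matches the mixed model only with equal caseloads and no participant-level covariates, so the two should not be treated as interchangeable.
- State which DDPPQ score is used (before training, six months after, change, or matched by date), and print the number of workers beside the estimate.
- If workers are few, report DDPPQ descriptively and draw no conclusion from it.

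The cost is revised wording and a somewhat more involved model, chiefly for PDA. The downside is a wider and probably inconclusive interval for the DDPPQ effect. With 8 workers, for example, a worker-level correlation would have to exceed 0.62 to pass the 0.1 threshold.
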